### **8.3.3.3. Immunogenicity**

Antidrug antibody concentrations in correlation with AGEN2034 PK exposure matrix will be summarized.

### **8.3.3.4. Exploratory Biomarkers**

Summary statistics for biomarkers will be provided for all preplanned time points. Changes from baseline for continuous biomarkers may also be presented as applicable and categorical biomarkers will be tabulated.

Possible relationship of biomarker levels with efficacy may be investigated.

## **8.3.4. Safety Analyses**

The extent of exposure to AGEN2034 will be characterized by duration (weeks), number of administrations, cumulative dose (mg/kg), dose intensity (mg/kg/week), relative dose intensity (actual dose given/planned dose), number of dose reductions, and number of dose delays.

Safety analyses will be performed on the safety analysis set. Safety endpoints will be summarized by dose cohort in each phase.

Safety assessments will be based on incidence of AEs, including AESIs, ADRs, immunogenicity, and changes in vital signs (including body weight), ECG, and laboratory values (hematology and serum chemistry).

The on-treatment period is defined as time from first dose of study treatment to last dose of study drug plus 30 days, or the earliest date of new anticancer therapy minus 1 day, whichever occurs first.

#### **8.3.4.1. Adverse Events**

Adverse events will be coded according to Medical Dictionary for Regulatory Activities (MedDRA) version 21.0. Severity of AEs will be graded using CTCAE (version 4.03) toxicity grading scale whenever possible.

Treatment-emergent AEs are AEs with onset dates during the on-treatment period, or the worsening of an event during the on-treatment period. Incidence of TEAEs, regardless of attribution, and AEs defined as related to AGEN2034 will be summarized by system organ class and preferred term, and described in terms of severity and relationship to AGEN2034.

Analysis of AES will be performed for events that are considered as treatment emergent. Adverse events leading to death or discontinuation of trial treatment, events with CTCAE Grade 3 or higher, study drug-related events, and SAEs will be summarized.

Indications of dose-related ADRs will also be examined.

#### **8.3.4.2. Laboratory Variables**

Laboratory results will be classified by grade according to NCI CTCAE. The worst on-trial grades after first trial treatment will be summarized. Shifts in toxicity grading from first treatment to highest grade will be tabulated. Results for variables that are not part of NCI CTCAE will be presented as below, within, or above normal limits. Only subjects with post-baseline laboratory values will be included in these analyses.

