### **5.5.2. Prohibited and/or Restricted Treatments**

As stated in the exclusion criteria ([Section 4.3](#)), subjects must not have had chemotherapy, radiotherapy (other than palliative bone-directed radiotherapy, as described in [Section 5.5.1](#)), major surgery, or received another investigational agent within 28 days before the start of study treatment.

Subjects are prohibited from receiving the following therapies and treatments during the Screening and Treatment periods of this trial:

- Immunotherapy not specified in this protocol.
- Chemotherapy.
- Investigational agents other than AGEN2034.
- Surgery for symptom management or tumor control.
- Growth factors (granulocyte colony-stimulating factor or granulocyte macrophage colony- stimulating factor). Exception: Erythropoietin and darbepoietin alpha may be prescribed at the investigator's discretion. Therapeutic use of G-CSF is allowed in subjects with Grade 3 or 4 febrile neutropenia.
- Radiation therapy for tumor control.
- Glucocorticoids for any purpose other than to modulate symptoms from an irAE, or for use as a pre-medication in subjects with a known history of an IV contrast allergy administered as part of computed tomography (CT) radiography.

Note: Replacement doses of corticosteroids (for example, prednisone 5-7.5 mg daily) are permitted while on study.

Note: Use of inhaled or topical corticosteroid is permitted.

- Bisphosphonates and/or receptor activator of nuclear factor kappa-B ligand (RANKL) inhibitor therapies cannot be initiated after informed consent has been signed. These therapies may be continued IF treatment with an agent from one of these two classes was initiated PRIOR to signing informed consent.
- Subjects who, in the assessment by the investigator, require the use of any of the aforementioned treatments for clinical management should be removed from the trial.
- Subjects may receive other medications that the investigator deems to be medically necessary.
- Medications listed in the Exclusion Criteria are prohibited in this trial.
- There are no prohibited therapies during the Post-Treatment Follow-up Phase

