Full serum chemistry 	X								X	X	X			
Hematology tests 	X		X	X			X	X	X	X	X			
Coagulation tests 	X			X			X		X	X	X			
Endocrine function tests 	X			X			X		X	X	X			
Urinalysis 	X			X			X		X	X	X			
Serum pregnancy test	X 													
Urine pregnancy test		X 					X		X	X	X			
Study drug administration 														
AGEN2034			X		X		X	X						

Abbreviations: ADA: anti-drug antibody; AEs: Adverse Events; d: day; ECG: electrocardiogram; ECOG: Eastern Cooperative Oncology Group; IERC: Independent Endpoint Review Committee; m: month; PBMC: peripheral blood mononuclear cell; PGx: pharmacogenomics; PK: pharmacokinetics; w: week.

Note: Where applicable, assessments performed prior to treatment unless otherwise indicated.

 All subjects who discontinue treatment will have at least one Follow-up Visit at 3 months (± 7 days) after last dose of study drug. Subjects who discontinue due to disease progression and/or start of a new line of therapy will then end participation in the trial. Subjects who received the maximum administrations of the combination of AGEN2034; who have achieved a complete response (CR) according to RECIST 1.1; or who have discontinued treatment due to reasons other than disease progression and/or start of a new line of therapy will be in Follow-up for up to approximately 12 months after last dose of study drug or until disease progression and/or start of a new line of therapy. Every effort should be made to collect subject information on the start of new antineoplastic therapy, disease progression and death.

 After the first Follow-up Visit, subjects that present(ed) with progressive disease and/or start new line of therapy will move into Survival Follow-up and should be contacted by telephone every 2 months for up to 12 months after last dose of study drug to assess for survival status. Post-study treatments and the subject's response to them will also be collected.

 Treatment administration and associated procedures for that visit may be delayed for treatment related AEs beyond the window and subsequent schedule adjusted accordingly.

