Unless otherwise stated, the number of subjects with an event (subject-wise) and the number of events (event-wise) will be provided for each summary.

Immune-related AEs will be tabulated using investigator-reported irAEs. .

Infusion related AEs will be tabulated using infusion-related reactions as reported by the investigators.

The following summaries by either SOC and PT or by PT and by toxicity grade will be provided. Summaries will be sorted by decreasing incidence of PT (within SOC, if applicable).

- TEAEs by SOC and PT, and by PT
- TEAEs by relationship to study drug, toxicity grade, SOC, and PT
- Drug-related TEAEs by SOC and PT, and by PT
- TEAEs leading to permanent treatment discontinuation by PT
- TEAEs leading to death by PT
- Drug-related TEAEs leading to permanent treatment discontinuation by PT
- Drug-related TEAEs leading to death by PT
- Serious TEAEs by SOC and PT, and by PT
- Serious TEAEs by relationship to study drug and toxicity grade, by SOC and PT
- Drug related serious TEAEs by SOC and PT, and by PT
- irAEs by SOC and PT, and by PT
- irAEs by relationship to study drug, toxicity grade, SOC, and PT
- Infusion-related TEAEs by SOC and PT, and by PT
- Infusion-related TEAEs by relationship to study drug, toxicity grade, SOC, and PT
- Laboratory abnormalities worsening (in at least one on-study measurement, relative to baseline) by NCI-CTCAE v4.03 criteria.
- ALT, AST, or bilirubin normal at baseline but with elevations $\geq 2 \times$ ULN.

The overall summary of will be reported by age (age < 55 vs age ≥ 55 , age < 65 vs age ≥ 65 , and age < 75 vs age ≥ 75), by race group including at least 5 subjects (groups < 5 subjects will be reported summarily as “Other”, patients treated in France who did not report race will be summarized as “Not reported (France)”), region (US vs EU vs other), and by normal vs abnormal creatinine and bilirubin levels at baseline.

In addition, the overall summary of AE incidence per month of drug exposure will be presented. Such a summary will report #patients/(total time of exposure in months) and #AEs/(total time of exposure in months.)

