7.6.4. Clinical Laboratory Tests

For clinical laboratory parameters, descriptive summary tables for observed values and changes from baseline will be provided by visit.

Laboratory values will also be categorized according to their NCI-CTCAE v4.03 toxicity grade, for the following parameters: ALT, AST, Bilirubin, Creatinine, Hemoglobin, Platelets, Neutrophils, and Lymphocytes. For applicable parameters, shift tables will be presented from the baseline toxicity grade to the worst post-baseline visit value (scheduled or unscheduled). All test results and associated normal ranges from local laboratories will be reported in SI units. All tests with numeric values will have a unique unit per test. Any laboratory test results and associated normal ranges from local laboratories will be converted to SI units. For the limited number of cases where the associated normal ranges from a local laboratory cannot be obtained despite due diligence, if query is unsuccessful at resolving issue and analysis is mandatory then the clinical scientist and medical monitor can provide a suitable normal range to be used in determining CTC grading and flags for above and below normal and the inferred normal range will be flagged in listings.

If a test value is reported with “<” or “>” sign (as below or above some detection limit), the test value will be imputed in summaries at the limit of detection (that is ignoring “<” or “>” signs), however the measurement will be listed as originally reported.

A standard ‘eDISH’ (evaluation of Drug-Induced Serious Hepatotoxicity) plot will be presented to display on the log-log scale the correlation between peak total bilirubin and alanine aminotransferase (ALT), both in multiples of ULN, with horizontal and vertical lines for Hy’s law thresholds, i.e., $3 \times \text{ULN}$ for ALT and $2 \times \text{ULN}$ for total bilirubin.

Listing will be provided for Safety Analysis Set.

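### Worst-grade, shift and worsening laboratory summaries do not stop at new anticancer therapy, so a 3-month follow-up value taken on the next therapy may become a subject's worst grade

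*Protocol*

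**What the plan says.** **Laboratory rules.** Protocol section 8.3.4.2: "The worst on-trial grades after first trial treatment will be summarized" and "Shifts in toxicity grading from first treatment to highest grade will be tabulated". For the graded parameters, SAP section 7.6.4 says "shift tables will be presented from the baseline toxicity grade to the worst post-baseline visit value (scheduled or unscheduled", and its eDISH plot uses peak bilirubin and ALT with no time limit. SAP section 7.6.2 adds a summary of "Laboratory abnormalities worsening (in at least one on-study measurement, relative to baseline) by NCI-CTCAE v4.03 criteria" and one of ALT, AST or bilirubin normal at baseline that reaches at least 2 x ULN. SAP section 5.5 admits unscheduled values to laboratory grading.

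**Time windows.** Protocol section 8.3.4: "The on-treatment period is defined as time from first dose of study treatment to last dose of study drug plus 30 days", or to the day before new anticancer therapy if that is earlier. Section 8.3.4.1 invokes this period for treatment-emergent AEs; section 8.3.4.2 does not mention it. SAP section 5.3 runs to 35 days after the last dose and SAP section 5.4 to 90 days. Neither stops at new therapy, and the SAP invokes both for AEs.

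**Visits.** Table 13, footnote 1: "All subjects who discontinue treatment will have at least one Follow-up Visit at 3 months". Those who stop for progression or a new line of therapy leave only after it. On what they may receive by then, protocol section 5.5.2 says: "There are no prohibited therapies during the Post-Treatment Follow-up Phase".

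**The concern.** The frequency, severity and duration of laboratory abnormalities is a named Phase 2 secondary endpoint, and the tables support the BLA filing analysis (SAP section 4.2). A worst-grade table takes a maximum over time, so its content depends on where the window ends. If the window runs past the start of the next treatment, a cytopenia or liver abnormality arising on that treatment can set the subject's grade. In a single-arm trial no comparator would show that this had happened.

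The AE rules are tighter. Under protocol section 7.2.1, AE reporting ends at 90 days or at new anticancer treatment, and after the Safety Follow-up Visit only treatment-related events are documented. The laboratory grades have neither a new-therapy stop nor an attribution filter, so AE and laboratory tables for the same subjects would describe different periods.

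**Working it through.** There is no stated figure to reproduce; this is a comparison of text plus day arithmetic.

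**1. Timing of Follow-up Visit 1.** Table 13 places it 3 months after the last dose, within 7 days either way. With the SAP's own conversion (30.4375 days per month, SAP section 7.2), 3 x 30.4375 = 91.3 days. The window is 91.3 - 7 = 84.3 to 91.3 + 7 = 98.3 days after the last dose.

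**2. Position against the defined periods.**

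| Period | Ends, days after last dose | Stops at new therapy? | Visit 1 relative to the end |
|---|---|---|---|
| Protocol 8.3.4, on-treatment | 30 | Yes | 54.3 to 68.3 days after |
| SAP 5.3, on-treatment | 35 | No | 49.3 to 63.3 days after |
| SAP 5.4, extended | 90 | No | 5.7 days before to 8.3 days after |
| Laboratory rules (on-trial, on-study, post-baseline) | No day stated | No | Inside |

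**3. What is drawn.** Table 13 marks full chemistry and hematology at the Discontinuation, Safety and first Follow-up visits. Its columns are broken in the text available to me; Table 11, which is more legible, shows the same pattern. The eight parameters graded in SAP section 7.6.4 (ALT, AST, bilirubin, creatinine, hemoglobin, platelets, neutrophils, lymphocytes) are all in those panels.

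**4. Who is there.** Table 13 footnotes 1 and 2 and protocol sections 6.3.4.1 (first paragraph) and 6.3.4.2 put the 3-month visit before the move to telephone survival follow-up, for subjects with progression or new therapy as well. Against this, section 6.4.1.9.1 moves Phase 2 subjects to survival follow-up once new therapy has started, and the Synopsis runs Follow-up Visits only until progression or a new line of therapy.

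**5. Direction.** Let W be a subject's highest grade up to the end of the on-treatment period and V the highest grade after it. The written rule reports max(W, V), which is never below W. Late values can add subjects to a high-grade row and cannot remove any.

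**6. Size.** The documents give neither the share of subjects on new therapy at Visit 1 (s) nor the chance that such a subject has a first Grade 3-4 value there (q). The number added to a Grade 3-4 row is 150 x s x q. As pure assumptions:

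- s = 10%, q = 5%: 150 x 0.10 x 0.05 = 0.75 subjects (0.5 percentage points).
- s = 50%, q = 40%: 150 x 0.50 x 0.40 = 30 subjects (20 percentage points).

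A range of about 1 to 30 subjects says only that the size is unknown. It also ignores deaths before Visit 1 and subjects still on drug at the cutoff.

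**The case against.** **The on-treatment period may already govern.** It sits in parent section 8.3.4, directly after the sentence that names laboratory values among the safety assessments. That reading is possible, but section 8.3.4.1 invokes the period expressly while section 8.3.4.2 uses the different term *on-trial*. The SAP then says *post-baseline* and *on-study*, and its own on-treatment period does not stop at new therapy.

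**Subjects on new therapy may have no clinic visit.** This stands in part. If section 6.4.1.9.1 and the Synopsis prevail, the scheduled exposure largely disappears and only unscheduled draws remain. The documents conflict, so one cannot say that contamination will occur.

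**Exposure is narrow.** This stands. The Safety Follow-up Visit must precede new therapy. What remains is one scheduled draw plus any unscheduled ones, and a value matters only if it is the subject's worst. *On-trial* and *on-study* also end with participation, but that outer limit still includes Visit 1.

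**The tables are descriptive.** This also stands. Grade and shift tables carry no causal attribution; causality is assessed through AEs (protocol sections 7.1.1 and 7.1.2). By-visit summaries and listings let a reader trace a Visit 1 value. A reader might infer that next-line toxicity is reported as caused by AGEN2034; the plan does not say that.

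**A long window suits a checkpoint inhibitor.** Protocol section 5.6 says immune-related events can occur several months after the last dose. This supports keeping late values visible. It does not support mixing in values taken on another treatment. A plain 90-day cut would also divide the Visit 1 window, as step 2 shows.

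**Conclusion.** The concern holds as a gap in the window definition. As written, the worst-grade, shift, worsening, 2 x ULN and eDISH summaries accept values taken after new anticancer therapy has begun. Under Table 13 and protocol sections 6.3.4.1 and 6.3.4.2, a scheduled draw exists at which this can happen. Any effect on the number of subjects with a high grade is upward.

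A reader might go further and infer that blood drawn on the next therapy is routinely counted, or that reported laboratory toxicity is inflated several-fold. The documents do not support either inference: the visit rules conflict, a late value counts only if it is the worst, and no document gives the rates needed for a multiplier. The primary ORR analysis is unaffected. The change is worth making because the endpoint is a named secondary one, the trial has no control arm, and the repair is cheap.

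**What to change.** 1. In protocol section 8.3.4.2 and SAP sections 7.6.2 and 7.6.4, limit the main worst-grade, shift, worsening, 2 x ULN and eDISH summaries to values from first dose to the end of the on-treatment period or the day before new anticancer therapy, whichever is first.
2. Use one on-treatment definition in both documents, with a new-therapy stop. When choosing its length, note that the Safety Follow-up Visit window reaches day 28 + 7 = 35, so a 30-day limit cuts through it.
3. Add a supplementary table of all later values before new therapy, covering the whole Visit 1 window, so that late immune-related abnormalities stay visible. List values taken after new therapy.
4. Reconcile section 6.4.1.9.1 and the Synopsis with Table 13 and sections 6.3.4.1 and 6.3.4.2 on whether subjects who have started new therapy attend the 3-month visit.

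The cost is a date filter, one extra table and wording. Subsequent therapy is already collected, and the SAP already uses its start date for BOR, DOR and PFS (sections 7.7.1, 7.7.3 and 7.7.9). The small downside is that a late drug-related abnormality moves from the main table to the supplementary table or, after new therapy, to the listing.

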#### **8.3.4.3. Physical Examination, Vital Signs, and Electrocardiogram**

Physical examination data, vital signs (body temperature, respiratory rate, heart rate, and blood pressure), and 12-lead ECG data will be presented.

### **8.3.5. Interim and Final Analysis**

Phase 2 is designed to have at least 2 interim analyses of the primary endpoint and selected secondary efficacy and safety endpoints. No early stopping for efficacy will be performed, as a more complete assessment of safety and durability of responses will be required for evaluation of risks and benefits. Consequently, the overall type I error will not be affected by the interim analyses. A non-binding futility analysis may be performed using methods described in the SAP.

The first interim analysis will be performed when data are available for approximately 30 subjects treated for at least 3 months. The primary analysis of efficacy and safety data will include all subjects dosed prior to a borderline date (specified as at least 3 months prior to the data cutoff). Another interim analysis will be performed 3 months after approximately 100 subjects have been dosed and will include, as the primary analysis of safety and efficacy, all subjects in the evaluable efficacy analysis set among the first approximately 100 subjects dosed. Sensitivity safety analyses

will be performed on all subjects in the safety analysis set dosed as of the data cutoff. Details of the interim analyses will be provided in a separate SAP.

Additional interim analyses for safety and efficacy assessment may be performed.

The final analysis will be performed after study completion.

The primary analysis set for efficacy assessment will be the evaluable efficacy analysis set. The primary analysis set for safety assessment will be the safety analysis set.

The interim analyses may include PD-1 expression data if available. Details will be provided in a separate SAP. After the interim analyses, subsequent enrollment of subjects may be based on biomarker enrichment (including but not limited to PD-L1 expression). In such cases, tumor tissue must be positive for the selected entry biomarker prior to subject enrollment.

## **9. TRIAL GOVERNANCE AND OVERSIGHT**

### **9.1. Safety Monitoring Committee**

A Safety Monitoring Committee (SMC) will regularly review safety data to ensure subjects' safety throughout the study.

The SMC will consist of permanent members from the Sponsor and/or CRO:

- Sponsor: head of development/chief medical officer, pharmacovigilance physician, study physician, and Principal Investigator(s).
- CRO: lead statistician and study physician.

During the Phase 1 portion of the trial, the SMC assess safety; decide on dose-escalation and opening of backfill enrollment; define the recommended Phase 2 dose (RP2D); and determine opening of the Phase 2 cohorts. The SMC recognizes that with the limited prior human experience with AGEN2034, a conservative approach will be adopted in ascribing the relationship of the treatment-related toxicity to the drug.

At each SMC review, all safety information of the participating subjects will be reviewed and the SMC will decide by consensus on continuation, modification, or suspension of the trial.

The SMC may modify the frequency of meetings as deemed appropriate during the course of the trial. The specific working procedures will be described in a separate SMC charter.

### **9.2. Independent Endpoint Review Committee**

For the Phase 2 portion of the study, a central facility will read and interpret all radiographic scans for subjects enrolled in the study. Data for all images will be transferred from trial sites to the central reading center for evaluation. Scans will be evaluated at the central facility in accordance with RECIST 1.1. Imaging data will be transferred to the designee at regular intervals. A manual from the vendor will be provided to each trial site.

For all subjects in Phase 2, the IERC will perform a blinded determination as to whether RECIST 1.1 criteria for tumor response or progression have been met. The IERC will be composed of a minimum of 3 properly qualified members.

The role of the IERC will be to review radiographic image findings for determination of the time point for overall response and date of disease progression (per RECIST 1.1) for each subject. The full membership, mandate, and processes of the IERC will be detailed in a separate IERC charter.

